## 8.4 Primary and Secondary Endpoint(s) and Associated Hypotheses

### 8.4.1 Primary Endpoint(s) and Associated Hypotheses

The primary endpoint is absolute value of the mechanical axis alignment. The mechanical axis alignment is defined as the angle between the line drawn from the center of the femoral head through the center of the knee and line drawn from the knee center to the ankle center. Mechanical axis alignment will be measured from weight bearing long-leg (51”) Anteroposterior (AP) radiographs, taken approximately 90 days post-op (when Subject has reached full knee extension, within 5 degrees) and read by an independent radiographic reviewer.

The mechanical axis alignment will be calculated from the Hip-Knee-Ankle (HKA) angle provided by the independent radiographic evaluations as:

$$\text{Mechanical Axis Alignment} = \text{HKA Angle} - 180.$$

The primary endpoint will be the absolute value of this Mechanical Axis Alignment result. Descriptive statistics for the primary endpoint will be presented by time point and treatment group.

The primary endpoint analysis will be to determine whether the mean alignment achieved with SUI instrumentation is non-inferior to the mean alignment achieved with RUI instrumentation. The non-inferiority margin was set at  $1.5^\circ$  based on clinical judgement as it was considered the maximum non-meaningful difference between instrumentation systems.

The null ( $H_0$ ) and alternate ( $H_A$ ) hypotheses are as follows:

$$H_0: \mu_{\text{SUI}} \geq \mu_{\text{RUI}} + 1.5^\circ$$

$$H_A: \mu_{\text{SUI}} < \mu_{\text{RUI}} + 1.5^\circ,$$

where  $\mu_{\text{RUI}}$  is the mean of the absolute values (hereafter, “absolute”) of mechanical axis alignment angle for Subjects being operated upon using reusable instruments

(RUI), and  $\mu_{SUI}$  is the mean of the absolute mechanical axis alignment angle of Subjects being operated upon using single use instruments (SUI).

#### **8.4.2 Secondary Endpoints and associated hypotheses**

The secondary endpoints are designed to further compare alignment achieved with SUI to that of RUI based on radiographs taken approximately 90 days post-op. The following secondary endpoints will be assessed:

- Difference in means (SUI-RUI) of the distal femoral varus-valgus (FM) angle,
- Difference in means (SUI-RUI) of the proximal tibial varus-valgus (TM) angle,
- Difference in means (SUI-RUI) of the femoral component flexion angle,
- Difference in means (SUI-RUI) of the tibial slope,
- Difference in means (SUI-RUI) of the raw mechanical axis alignment angle.

The calculations of these endpoints from the independent radiographic evaluations is as follows:

1. Distal femoral varus-valgus angle: The result from the independent radiographic evaluations will be used without change.
2. Proximal tibial varus-valgus angle: The result from the independent radiographic evaluations will be used without change.
3. Femoral component flexion angle:
  - a. For CR configuration, the femoral component flexion angle to be used in the analysis = 95 – the femoral component flexion result provided in by the independent radiographic evaluation.
  - b. For PS configuration, the femoral component flexion angle to be used in the analysis = 77 – the femoral component flexion result provided in by the independent radiographic evaluation.

4. Tibial slope: the tibial slope to be used in the analysis = 90 – the tibial slope result provided by the independent radiographic evaluation.
5. Raw mechanical axis alignment angle: The raw mechanical axis alignment angle will be calculated from the Hip-Knee-Ankle (HKA) angle provided by the independent radiographic evaluations as:

$$\text{Mechanical Axis Alignment} = \text{HKA Angle} - 180.$$

Descriptive statistics for the secondary endpoints will be presented by time point and treatment group.

For each of the above endpoints, an exploratory two sample, 2-sided t-test will be conducted to test ( $H_0$ ) versus alternate ( $H_A$ ) at the  $\alpha = 0.05$  level:

$H_0: \mu_{SUI} = \mu_{RUI}$

$H_A: \mu_{SUI} \neq \mu_{RUI}$ , where  $\mu_{SUI}$  is the mean of the angle/slope for Subjects treated with SUI and  $\mu_{RUI}$  is the mean of the angle/slope for Subjects treated with RUI.

In addition, the distributions of the raw values (showing both positive and negative results, where appropriate) associated with these endpoints will be summarized as categorical variables (n, %) in 1-degree increments, and the relative frequencies will be graphed by treatment group for the following measurements:

- Absolute mechanical axis alignment angle;
- Distal femoral varus-valgus (FM) angle;
- Proximal tibial varus-valgus (TM) angle;
- Femoral component flexion angle;
- Tibial slope angle; and
- Raw mechanical axis alignment angle.

Additionally, a third analysis will be conducted to present the number of surgeries achieving the Mechanical Axis Alignment within 3 degrees of target (i.e.,  $\pm 3$  degrees

of 0) at 3 Months post-operative. These results will be presented categorically (n, %) by treatment group and by site (i.e., surgeon).

### **8.4.3 Additional Endpoints (Primary, Safety, or Exploratory)**

#### **Surgeon Satisfaction**

Surgeon satisfaction with the performance of SUI and RUI instrumentation will be assessed on a four-point scale (1=Strongly Dissatisfied, 2=Dissatisfied, 3=Satisfied, 4=Strongly Satisfied) for the following:

- Distal femoral resection instrumentation;
- Proximal tibial resection instrumentation; and
- All ATTUNE TKA instrumentation.

For each of the three satisfaction questions above, analysis will be conducted two ways:

- (1) Summarizing the response to each question as a categorical variable: The tally and percent of times that each response was indicated. This will be summarized overall and by site.
- (2) Dichotomizing the response to determine “Adequate Surgeon Satisfaction” then summarizing by treatment group with counts and percentages. Adequate Surgeon Satisfaction will be derived as “Yes” for responses: “Satisfied” and “Strongly Satisfied” and “No” for responses: “Strongly Dissatisfied” and “Dissatisfied”. Binomial exact 95% CI will be provided for the proportions and fisher’s exact test will be implemented to test the difference between treatment groups.

For each site (surgeon), a line graph will be generated which displays surgeon satisfaction (y-axis) for the site’s first through last case (x-axis).

## **OR Efficiency**

Exploratory analyses will be conducted to see if SUI improves OR efficiency compared to conventional (RUI) instruments. Specifically, the following durations will be assessed comparatively between treatment groups and stratified by site:

- OR Set-up Time: Set-up Stop Time – Set-up Start Time;
- Anesthesia Time: Anesthesia Stop Time – Anesthesia Start Time;
- Surgery Time: Surgical Stop Time – Surgical Start Time;
- Clean-Down Time: Clean Down Stop Time – Clean Down Start Time;
- Total Time: Clean Down Stop Time – Set-up Start Time.

For each of the OR Efficiency endpoints defined above, analysis will be conducted by summarizing the endpoint as a continuous result (n, mean, SD, median, min, max, 95% CI) and presenting results by treatment group. In this analysis, 2 sample t-tests will be used to assess the difference in the mean response between treatment groups.

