4.2 Study Design Rationale

The study was designed as comparative, sequential, non-randomized, multi-center, such that each site has an equal number of Subjects in each treatment group, SUI and RUI. The follow-up period of approximately 90 days was selected due to the time required for most Subjects to be able to achieve full leg extension (within $\pm 5^\circ$), a requirement for obtaining suitable weight-bearing hip-to-ankle radiographs for analysis of alignment. The mechanical axis alignment will be assessed at the 3 month follow-up by independent radiographic review. The sequential design (that is at each site all RUI cases will be completed before doing any of the SUI cases) is set up to ensure that with the control group (RUI), current status of OR efficiency is captured rather than this being influenced by any efficiencies learned from use of the SUI.

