7 STUDY DESIGN

This study is designed as a prospective, comparative, sequential, non-randomized, multi-center, controlled clinical investigation.

There will be 4 centers worldwide that will recruit a total of 88 Subjects (44 Treatment Subjects and 44 Control Subjects). A complete description of the methods for determining sample size is contained in Section 10.9. Initially, the Subjects will be evenly distributed across the four sites; therefore it is expected that each site will recruit 22 Subjects (11 Control followed sequentially by 11 Treatment Subjects). In between the Control and Treatment Subjects, a learning curve is permitted for the use of SUI.

- The **Control group** will consist of 44 Subjects, 11 per site and the surgical procedure for these Subjects will be performed using Reusable Instruments (RUI).
- The **Treatment group** will consist of 44 Subjects, 11 per site and the surgical procedure for these Subjects will be performed using Single Use Instruments (SUI).

At each site the 11 Control Subjects will be enrolled and operated on prior to performing the first surgery in the Treatment group. For a given site, either Cruciate Retaining or Posterior Stabilising configurations will be used; consistent with their standard of care. Within a given CR site, the Investigator may choose to implant either the CR FB or CR RP. Similarly, within a given PS site, the Investigator may choose to implant either the PS FB or PS RP. Randomization is not being applied in this study in order to isolate and learn if there are changes in OR efficiency with SUI under normal operating room procedures.

One surgeon at each site will complete all RUI and SUI surgical cases including the learning curve. No Sub-Investigators will be permitted to perform surgery to avoid possible confounding issues with varying surgical process. All sites will have previously completed their learning curve with the ATTUNE Primary Implant implanted using RUI prior to enrolling the 1st patient. Then after the completion of all RUI study cases, a learning curve will be permitted for the use of SUI. The duration of the SUI learning curve is anticipated to be approximately 5 cases and is at the discretion of the Principal Investigator. These early cases that are within the learning curve will not be enrolled into this study at each site.

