### **Procedural Delays**

The incidence of procedural obstacles (i.e., Staff change-over, Holes in blue wrap, Late staff, Missing instrument(s), Missing implants, Patient delay, Prolonged anesthesia, Prolonged surgery, Scrub nurse not familiar with instruments, or Other) will be summarized for both treatment groups.

For each site (surgeon), a listing of procedural obstacles will be generated which presents the procedural obstacles for the site's first through last case.

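### OR times are tested with no time or case-order term although every SUI case at a site follows every RUI case, so the result is a difference between phases and cannot be attributed to the instruments alone

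*SAP*

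**What the plan says.** SAP 8.4.3, OR Efficiency, sets out to learn whether SUI improves efficiency over RUI on five durations: set-up, anesthesia, surgery, clean-down and total time. The comparison is structured by group and site: "the following durations will be assessed comparatively between treatment groups and stratified by site". The test is given as: "In this analysis, 2 sample t-tests will be used to assess the difference in the mean response between treatment groups". Protocol 10.10 adds exploratory work on step times, inter-site differences and delays, but no time trend.

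The order of cases is fixed. Protocol 4.2 explains the sequential design: "that is at each site all RUI cases will be completed before doing any of the SUI cases". Protocol 7 repeats it with numbers: "At each site the 11 Control Subjects will be enrolled and operated on prior to performing the first surgery in the Treatment group". About 5 unenrolled SUI learning cases per site fall between the two phases (Protocol 7, SAP 1).

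Two reasons are given for this design. Protocol 7 says: "Randomization is not being applied in this study in order to isolate and learn if there are changes in OR efficiency with SUI"; SAP 1 has a matching sentence. Protocol 4.2 says the order ensures that, for the control group, "current status of OR efficiency is captured rather than this being influenced by any efficiencies learned from use of the SUI".

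For two other exploratory endpoints the SAP does look at sequence. Surgeon satisfaction is graphed by case within site, and a listing by site "presents the procedural obstacles for the site's first through last case". Nothing similar is planned for OR times.

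**The concern.** Within each site, SUI also means later. A two-sample t-test then estimates the instrument effect plus whatever else changed between the phases: staff getting used to being timed, turnover in the theatre team, or altered cleaning or anesthetic practice. Three of the four timed elements (set-up, anesthesia, clean-down) depend largely on people other than the surgeon.

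The stated rationale in Protocol 4.2 guards in one direction only. It keeps efficiencies learned from SUI out of the RUI data. It does nothing about change that runs forward from the RUI phase into the SUI phase.

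The endpoint is exploratory, but OR efficiency is the reason given for leaving out randomization, and the sponsor commits to publishing the study (Protocol 13.8). A p-value below 0.05 could be presented as evidence that SUI improves efficiency when it shows only that later cases ran faster or slower.

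**Working it through.** **Figures in the plan.** The documents state no SD, effect size, power or drift for OR times, so there is no figure of the plan's own to reproduce on this point. (The stated 95% power with 35 per group concerns the alignment endpoint. It reproduces at 95.3% by the noncentral t and has no bearing here.) Everything below is in within-group SD units over an assumed range.

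**Inputs.**
- 44 per group; 4 sites, each with 11 RUI then 11 SUI (Protocol 7, SAP 1). OR times use the Safety Set (SAP 6.2), so the full 44 is used.
- Two-sided alpha 0.05 (Protocol 10.3; sidedness assumed from the 2-sided 95% intervals).
- Gap of g unenrolled cases between phases; g = 5 is the anticipated number, 0 and 10 are taken as a range.
- No true instrument effect.

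**1. A shared shift of d SD between phases, planned test.** The noncentrality is d / √(2/44) = d / 0.2132, with 86 df.

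| d (SD) | noncentrality | rejection rate |
|---|---|---|
| 0.14 | 0.66 | 10% |
| 0.2 | 0.94 | 15% |
| 0.3 | 1.41 | 29% |
| 0.5 | 2.35 | 64% |

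**2. A linear drift of b SD per case.** The phase means are 11 + g cases apart, so the bias is b × (11 + g). With g = 5 this is 16b.

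| b (SD per case) | bias (SD) | rejection rate |
|---|---|---|
| 0.01 | 0.16 | 12% |
| 0.02 | 0.32 | 32% |
| 0.03 | 0.48 | 60% |

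A simulation with 20,000 replicates gave the same rates. At b = 0.02 the rate is 17.5% for g = 0 and 49% for g = 10.

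**3. Stratifying by site.** Every site has the same order, so each within-site difference carries the same bias of 16b. A single-site 11 v 11 test rejects less often (11% at b = 0.02) only because it is smaller.

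**4. What a case-order term can do.** Take a model with site, instrument and linear case order. The correlation r between instrument and order is 0.87 (g = 0) or 0.93 (g = 5). The variance inflation 1/(1 − r²) is 4.0 or 7.4, so the interval is √4.0 = 2.0 or √7.4 = 2.7 times as wide.
- Linear drift: bias returns to about 0 and rejection to about 5% (4.8% to 5.3% in simulation, g = 5).
- Step change at the switch: the bias stays in full. The standard error is 0.2132 × 2.72 = 0.58 SD, so a 0.3 SD step is rejected about 8% of the time and a 0.5 SD step about 14%. The fall from 29% and 64% comes from the wider interval, not from removing bias.
- Power (g = 5): a real 0.6 SD difference is detected about 18% of the time, against 79% with the planned test.

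**5. What the RUI phase alone shows about drift.** The within-site sum of squares of case order is 110 for 11 cases, or 440 over 4 sites. The slope standard error is 1/√440 = 0.048 SD per case, and the 95% half-width is about 0.096 (39 df). Power to detect drifts of 0.01, 0.02 and 0.03 is about 5%, 7% and 9%.

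**The case against.** The strongest reply is about weight. SAP 5 says only the primary analysis is powered, treats all other p-values as exploratory and rules out labeling claims from them. Protocol Table 10-2 lists OR efficiency as exploratory with no difference expected. The sequential design is disclosed and labelled Level III evidence. One surgeon per site does all cases, RUI learning is complete beforehand, SUI learning cases are excluded, and enrollment is planned for 8 months. Obstacles such as staff change-over and prolonged anesthesia are already listed in case order.

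Much of this stands. It limits the consequence to interpretation and publication, and it reduces surgeon learning as a source of drift. It does not cover set-up, anesthesia or clean-down, and it does not make the design able to isolate an instrument effect.

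A second reply is that a case-order model is no cure. This also stands. A reader might infer that adding such a term returns the error rate to 5% for any shift. That holds only for linear drift: a step at the switch cannot be told apart from SUI, and new staff or a changed cleaning routine could well act as a step. A reader might also infer that the 44 RUI cases show how much drift there was. With a half-width of 0.096 SD per case, they say almost nothing about drifts of the size considered here. Letting significance in the adjusted model decide the wording would demote most real effects.

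**Conclusion.** The point holds as one about analysis and interpretation. The planned comparison has no time term, instrument and phase coincide within every site, and stratifying by site leaves the problem untouched. The claim in Protocol 7 and SAP 1 that the design isolates OR-efficiency changes with SUI is not supported.

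The size depends on an assumed shift: about 10%, 29% or 64% rejection at 0.14, 0.3 or 0.5 SD, with 44 per group and no true effect. A reader might go further and conclude that the OR-time result will be biased in favour of SUI. The documents do not support that: they give no OR-time SD or trend, and drift could run in either direction. Nor does this point touch the power of the primary alignment endpoint.

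**What to change.** 1. In SAP 8.4.3, OR Efficiency, add a plot of each of the five durations by within-site case order or surgery date, in line with the displays already planned for satisfaction and obstacles.
2. Keep the planned t-test. State beside it that the result is a difference between sequential phases that cannot be attributed to the instruments alone, whatever its p-value. Amend the isolation wording in Protocol 7 and the matching sentence in SAP 1.
3. As a sensitivity analysis only, report the instrument difference with a 95% CI from a model with site, instrument and linear case order, numbered through the learning-case gap (or surgery date, if the number of learning cases is not recorded). State that it corrects linear drift only, cannot separate a step change at the switch from SUI, and has an interval about 2.0 to 2.7 times as wide. Do not make significance in this model a condition for any wording.

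The cost is one extra figure and one extra model per duration, some rewording in both documents, and a less favourable efficiency statement. Surgery dates should already be held, and the by-case displays already planned need the case sequence, so no new data collection is expected.

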Both resurfaced patellae and non-resurfaced patellae are permitted in this investigation, consistent with site standard of care. TruMatch technology or any other type of Custom Patient Instruments are not permitted. Similarly Computer-Assisted Surgery (CAS) is not permitted within the study. The procedures must be performed using only the instrumentation provided (SUI or RUI) and standard surgical methods, without additional tools that could confound the key research question of this study (for example, instrumentation that helps perform bone resections).

The Sponsor will monitor overall project enrollment. Cohort reallocation during the RUI phase only may be done in order to maintain project timelines. The Sponsor can authorize a shift of a group of Subjects from one site to another to maintain project timelines. For example, the Sponsor can reduce the cohort of a slow-enrolling RUI site to a faster-enrolling RUI site and the faster-enrolling RUI site will assume responsibility for the reallocated RUI cohort and the same number of SUI Subjects.

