8.3.3 Intra-operative Management

The surgical process is to follow site standard of care.

This investigation allows the Investigator to follow their current standard of care with respect to patellar resurfacing. Specifically the Investigator can choose to:

[figure not shown]
- Resurface the patella
- Leave the patella unresurfaced.

This investigation does NOT permit the Investigator to use TruMatch (or any other PSI instrumentation) or CAS for any Subjects, whether they are in the RUI or SUI arms of the study.

Products supplied by DePuy Synthes must be used in accordance with the manufacturer’s instructions unless an alternative technique is medically necessary.

Each Investigator or designee will collect information as noted in Table 8-3 below. The detailed surgical procedure is provided in Exhibit B. Data collection will begin at the time the OR is being set up for a study Subject procedure and will continue until the room is cleaned up and ready for the next case.

Table 8-3: Intra-operative Data Collection and eCRFs

Evaluation	Details of Evaluation
Operative Details eCRF	
For all Subjects, detailed surgical information and time information relating to the duration of 4 key elements of the surgical procedure will be recorded on the Operative Details eCRF. These 4 elements are OR Set Up, Anesthetic, Surgery & Clean Down. Definitions of each element will be provided as part of the training for individuals who will be capturing time data. Note there is likely to be overlap in time between some of these elements (possible scenario illustrated below).
  
In addition to the start and stop times for the 4 key elements, the occurrence of various incidents that can introduce delays or interruptions to the surgical flow will also be recorded.

Evaluation	Details of Evaluation
Device Log eCRF	For all Subjects , each component used during the procedure should be documented on the Device Log eCRF. The required product codes and catalog numbers can be found on pre-printed labels provided in the sterile implant boxes. Retain a copy of each label to facilitate data entry into the eCRF

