11.1.2 The ATTUNE Single Use Instruments (SUI)

The ATTUNE Single-Use Instruments (SUI), which are also referred to as SOLO, as used on the Treatment group, will be used on a single patient and then disposed of. Single-Use instruments are manufactured from engineering grade polymers and supplied sterile packed to hospitals. Kits consist of 5 packs, which contain all of the necessary instruments to perform a Total Knee Arthroplasty. The pack details are outlined in Table 11-1 below. Once a procedure is complete the packs of instruments are disposed of in clinical waste. Details of the Packs and their function are outlined below.

Table 11-1: Detailed Instrument Information by Pack

Single Use Instruments: Complete set is delivered in 5 Packs

1 – Primary Cuts & Sizing	Indication: Enables distal femoral and proximal tibial cuts, plus sizing of both femur and tibia.
2 – Tibial Preparation	Indication: Provided in 6 sizes, with one pack being opened once the patient anatomy is defined.
3 – Femoral Finishing	Indication: Provided for both CR and PS configurations, each available in 6 sizes. The specific size and configuration dictates which pack is opened.
4 – Patella Preparation	Indication: Used to size the patella and fix the patella implant component.
5 – Pin Pack	Indication: Used for pinning throughout the procedure.

[figure not shown]

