## 8.3 Demographic and Baseline Characteristics

Descriptive statistics will be displayed using the subjects in the Safety and the Per Protocol Analysis Populations for:

- Age at consent (in years);
- Gender;
- Race;
- Ethnicity;
- Height (cm);
- Weight (kg);
- BMI ( $\text{kg/m}^2$ ) calculated as  $(\text{Weight in kilograms})/(\text{Height in meters})^2$ ;
- Primary Diagnosis;
- Configuration type (Cruciate Retaining or Posterior Stabilizing);
- Breakdown of Fixed Bearing and Rotating Platform configurations within CR and PS.

Preoperative demographics and baseline characteristics will be compared to determine whether differences exist between treatment groups. Operative details including the type of components implanted, configuration type, and breakdown of FB and RP configurations within CR and PS will be presented without formal comparison.

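### Surgery Time and Total Time are compared with no account of patellar resurfacing, so a within-site change in resurfacing rate between the RUI and SUI phases would be read as an instrument effect

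*SAP*

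**What the plan says.** - **Analysis.** SAP 8.4.3 (OR Efficiency) defines five durations, including Surgery Time and Total Time. It says that "the following durations will be assessed comparatively between treatment groups and stratified by site", and then that "2 sample t-tests will be used to assess the difference in the mean response between treatment groups". Resurfacing is neither a stratum nor a model term.
- **Resurfacing policy.** Protocol Section 7: "Both resurfaced patellae and non-resurfaced patellae are permitted in this investigation, consistent with site standard of care". Protocol 8.3.3: "This investigation allows the Investigator to follow their current standard of care with respect to patellar resurfacing"; it then lists resurfacing and leaving the patella unresurfaced as the two options.
- **Contrast with implant configuration.** Protocol Section 7 does restrict configuration by site: "For a given site, either Cruciate Retaining or Posterior Stabilising configurations will be used; consistent with their standard of care". No similar rule covers the patella, either by site or across phases.
- **Extra step.** Protocol Table 11-1 describes a separate patella pack among the single-use instruments: "Used to size the patella and fix the patella implant component".
- **Data capture.** Protocol 8.3.3, for all Subjects: "each component used during the procedure should be documented on the Device Log eCRF".
- **Display.** SAP 8.3 covers "Operative details including the type of components implanted, configuration type" and the bearing breakdown, presented descriptively with no formal comparison and no link to the time analyses.
- **Sequence and status.** Each site completes its 11 RUI cases before its first SUI study case, without randomization (Protocol Sections 4.2 and 7). SAP Section 5 treats everything except the primary endpoint as exploratory and rules out labeling claims from it.

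**The concern.** Sizing the patella, preparing it and fixing a cemented component takes time that falls within Surgery Time, and therefore within Total Time. Because instrument type and calendar phase coincide at every site, a surgeon who resurfaces more often, or less often, in the second phase shifts the SUI mean for a reason that need not be the instruments. A rise would make SUI look slower and a fall would make it look faster. The planned test cannot tell either from an instrument effect.

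This matters more than a typical exploratory covariate for two reasons. First, learning about OR efficiency is the protocol's stated reason for the sequential, non-randomized design (Sections 4.2 and 7). Second, the protocol already accepts the principle: it excludes simultaneous bilateral procedures because their longer duration would confound the timing data (criterion 5.2 k and its footnote). Resurfacing is a smaller instance of the same problem, and it is recorded but not used.

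**Working it through.** **The plan's own figures.** The documents give no SD, effect size or power for any OR time. The only sample-size figure concerns alignment: SD 1.87°, margin 1.5°, 1-sided alpha 0.05 and 35 per group give 95.3% power by the noncentral t (stated 95%), and 35/(1 − 0.20) = 43.75, rounded up to 44. That reproduces. Only the 44 per group is used below.

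**Inputs**
- From the documents: 4 sites, 11 RUI then 11 SUI per site, 44 per group, 2-sample t-test.
- Assumed, because the documents are silent: minutes per resurfacing *m* = 5 to 10; within-site change in resurfacing rate Δ = 10 to 30 points; SD of the duration 15 minutes.

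**Step 1: size of the bias.** With no true instrument effect, the expected SUI minus RUI difference is Δ × *m*.
- Low end: 0.10 × 5 = 0.5 min.
- High end: 0.30 × 10 = 3.0 min.
- Standard error: 15 × √(2/44) = 3.2 min.

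**Step 2: effect on the test.** Two-sided 0.05 t-test, 44 per group, SD 15, noncentral t:

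| Spurious difference | False-positive rate |
|---|---|
| 0.5 min | 5.3% |
| 1.5 min | 7.5% |
| 3.0 min | 15% |

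**Step 3: does site stratification remove it?** Simulation with 4,000 runs, 4 sites with assumed different mean times, 10 min per resurfacing, residual SD 15 and no instrument effect:

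| Scenario | Analysis | Bias (min) | Rejection |
|---|---|---|---|
| Rate 40% to 70% at each site | Pooled t-test | 3.0 | 10% |
| | Site-adjusted | 3.0 | 14% |
| | Site + resurfacing | 0.0 | 5.1% |
| Resurfacing constant within each site | Pooled t-test | −0.02 | 4.5% |
| | Site-adjusted | −0.02 | 5.2% |

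Site adjustment leaves a within-site change untouched. With constant practice there is nothing to correct.

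**Step 4: is a resurfacing term alone enough?** No. Suppose resurfacing rises from 70% to 100% at two sites and from 0% to 30% at the other two, with 10 min per resurfacing, and the higher-resurfacing pair is 20 min slower for other reasons. Let *g* be instrument group, *p* resurfacing and *A* the slower pair.
- var(*g*) = var(*p*) = 0.25.
- cov(*g*, *p*) = 0.30 × 0.25 = 0.075.
- cov(*A*, *g*) = 0.
- cov(*A*, *p*) = 0.5 × 0.85 − 0.5 × 0.5 = 0.175.
- With site omitted, the coefficient of *A* on *g* given *p* is −(0.075 × 0.175)/(0.25² − 0.075²) = −0.0131/0.0569 = −0.231.
- Bias in the instrument effect: 20 × −0.231 = −4.6 min, against +3.0 min with no adjustment.

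The model therefore needs both site and resurfacing.

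**The case against.** The strongest reply is that the condition may never arise. One surgeon per site performs all RUI and SUI cases, resurfacing is tied to site standard of care, and enrollment is expected to take 8 months. Group sizes are equal within site, and any reallocated RUI cohort brings the same number of SUI Subjects. A surgeon with a settled practice contributes no bias. This stands as a limit on the point, but not as an answer to it: neither document requires practice to be constant, although configuration is explicitly constrained by site.

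A reader might infer three stronger things that the documents do not support.
- **That resurfacing is decided case by case.** The text permits this but does not say it.
- **That the time comparison ignores all structure.** It is stratified by site, which allows for customs that differ between surgeons.
- **That the study's conclusions are at risk.** OR time is exploratory, and nothing here bears on the alignment endpoint.

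It is also fair to say that the magnitude is entirely assumed and, over the range used, below one standard error. The component listing in SAP 8.3 might reveal a shift in rates; the table shells are a separate document, so this cannot be confirmed. Revealing a shift would still not correct the time estimate.

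Two further objections bear on the remedy. Bearing type or BMI could also differ between phases; that is true, but resurfacing is itself an added timed step. And resurfacing may be chosen after the instrument type is known, so adjustment could remove a real part of the instrument effect. That stands, and it is why the planned result should be kept.

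**Conclusion.** The point holds in conditional form. If the resurfacing rate changes within sites between phases, the planned comparison of Surgery Time and Total Time attributes the change to the instruments, and site stratification does not prevent this. The bias is zero at a site that always or never resurfaces. Otherwise it is the rate change multiplied by the minutes per resurfacing: 0.5 to 3 minutes under the assumed 5 to 10 minutes and 10 to 30 points, with a false-positive rate of about 5% to 15% at an assumed SD of 15 minutes. None of those three inputs is in the documents, and neither the size nor the direction of any change can be derived from them. Because the endpoint is exploratory and supports no labeling claim, this is a low-cost improvement and not a defect that threatens the study.

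**What to change.** In SAP 8.4.3 (OR Efficiency):

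1. Keep the planned comparison as written.
2. For Surgery Time and Total Time, add an SUI minus RUI difference with 95% CI from a linear model with terms for instrument group, site and patella resurfaced (yes/no, derived from the Device Log). State that if resurfacing does not vary within any site, the term is redundant with site and is dropped.
3. Report the resurfacing rate by group and site with these results. If the rates are constant, that table closes the question.
4. Present both estimates, noting that the adjusted one excludes any effect of instrument type that acts through the decision to resurface.

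**Cost.** SAP wording and one additional model. It needs no new data, no extra Subjects and no change to surgical practice. Residual degrees of freedom fall from 86 (88 − 2) to 82 (88 − 6: intercept, group, three site terms, resurfacing). The real downside is the one in item 4, which showing both estimates addresses.
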